While drug demand plotted as a function of unit price has been often shown to be a function of the total drug consumed, there is some research with cigarette demand that call this finding into question. The most prominent of these is a study by Johnson et al. (2004) that compared conventional cigarettes to denicotinized cigarettes. They found that, if they were the only tobacco product available, the denicotinized cigarettes had comparable demand to nicotinized cigarettes. If both were available, participants preferred the nicotinized cigarettes. This suggests that cigarette demand is not strictly regulated by nicotine dose, and that there is substantial abuse liability associated with the cigarettes themselves apart from any nicotine content.

The specific objective in the proposed research is to examine the effect of nicotine content (0.4 mg/g, 1.4 mg/g, 2.5 mg/g, 5.6 mg/g, and 17.4 mg/g of tobacco) and blood nicotine absorption on laboratory behavioral economic measures of demand intensity and elasticity. Under double-blind conditions, we will examine the relationship between plasma nicotine and cigarette demand as a function of the dose of the nicotine in the cigarettes. Regular cigarette smokers will consume, on separate sessions, controlled puffs of a cigarette containing a blinded dose of nicotine then complete a cigarette purchase task, our measure of value, while plasma nicotine is measured. We hypothesize that cigarette demand will be associated with dose and level of circulating nicotine, but in a nonlinear fashion such that consumption of very low dose cigarettes will not be predicted by nicotine dose or intake alone.

2.2 EXPLAIN WHAT THE RESEARCH TEAM PLANS TO DO WITH THE STUDY RESULTS:

For example - publish or use for dissertation

The research team intends to publish the results of the current study in peer-reviewed journals.

Section 3: Recruitment

3.1 DESCRIBE THE SUBJECT POOL, INCLUDING INCLUSION AND EXCLUSION CRITERIA AND NUMBER OF SUBJECTS:

Examples of inclusion/exclusion criteria - gender, age, health status, ethnicity

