Seven Cigarette purchase sessions (approximately 1.5 hours). In the remaining seven cigarette purchase sessions (may be more than 7 due to factors outside of the control of participants, for example, a participant is eligible to start a purchase session but blood is unable to successfully be drawn), we will assess the behavioral economic demand intensity and elasticity of cigarettes with different nicotine concentrations. During each of these 7 cigarette purchase sessions, participants will consume either their usual brand of cigarette, an experimental cigarette containing 0.4 mg/g, 1.4 mg/g, 2.5 mg/g, 5.6 mg/g, or 17.4 mg/g nicotine, or a nonusual brand, commercially available cigarette. All but the nonusual brand, commercially available cigarettes will be presented in a randomized order across participants to control for any order effects; the nonusual brand, commercially available cigarette will be administered during the 7th session. The participants' preferred brand of conventional cigarettes will be used for the appropriate session. The cigarette doses will be blinded so the participants are not aware of the dose they will administer, leaving only subjective effects. Participants will be asked to abstain from consuming nicotine for 12 hours prior to each cigarette purchase session. Abstinence will be verified with breath CO at the beginning of the session, which will need to be <8 ppm to participate. If participants do not meet this criterion, they will be allowed to reschedule the session and try again. After repeated failed attempts, participant participation may be terminated. Each purchase session will begin with baseline ratings of nicotine craving, current drug effect, breath CO, and nicotine withdrawal symptoms. The baseline blood draw will also be collected at this time. Blood will be drawn with a catheter throughout the session by a registered nurse or other personnel with phlebotomist training to measure plasma nicotine levels during the sessions. The catheter will be removed at the end of each purchase session. Snacks and/or beverages will be available for the participants to consume, at their own discretion, should they begin to feel light-headed.

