For Aim 1 we request a sample size of $n=36$ completed participants. In this aim, we intend to compare demand for cigarettes across doses of nicotine. Typically, demand for a drug is not compared across doses because when price is expressed as unit dose (expenditure per mg of drug), all reinforcing doses of a drug fall on the same demand curve (Hursh & Silberberg, 2008). However, here we are explicitly intending to assess where the low-dose effect occurs for cigarettes (i.e., the dose at which consumption data no longer falls on the same unit-price curve), so we will compare demand across doses. A reanalysis of previous work (Johnson, et al., 2004) that compared demand for conventional and denicotinized cigarettes resulted in a very large effect size, which would be expected with cigarettes containing negligible amounts of nicotine. These data do not form a good basis for the present power analysis as they are an extreme case. Therefore, we have powered Experiment 1 to give us an 80% chance to detect an effect size of $f = 0.175$, which lies half way between a 'medium' and 'small' effect by convention (Cohen, 1992). This analysis was based on a within-factors ANOVA with 6 repeated measures (doses) per subject and a type 1 error rate of $\alpha = 0.05$, calculated in G*Power 3.1.9.2.

Data Analyses

Demand Analyses by Nicotine Content. In this experiment, we will compare behavioral economic demand intensity and elasticity of conventional cigarettes and reduced-nicotine cigarettes at five doses (0.4 mg/g, 1.4 mg/g, 2.5 mg/g, 5.6 mg/g, and 17.4 mg/g). Demand data will be fit to a modification (Koffarnus, et al., 2015) of a model proposed by Hursh and Silberberg (2008) to quantify the relationship between the price of a commodity and consumption of that commodity:

$$Q = Q_0 * 10^{k(e^{-\alpha Q_0 C} - 1)}$$

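### Experiment 1's 80% power belongs to a six-level comparison of cigarette types; for the five-dose comparison it is presented as covering, power is about 75% at the same effect size, and no five-dose test is prespecified

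*Combined protocol and SAP*

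**What the plan says.** The Sample Size Justification for Experiment 1 sets the aim as a comparison of demand between nicotine doses, to locate the dose at which the low-dose exception begins. It continues: "For Aim 1 we request a sample size of $n=36$ completed participants", and "we have powered Experiment 1 to give us an 80% chance to detect an effect size of $f = 0.175". The calculation is a "within-factors ANOVA with 6 repeated measures (doses) per subject" at alpha 0.05 in G*Power. Neither the correlation between repeated measures nor the nonsphericity correction is given.

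Elsewhere the number of doses is five. Section 2.1 of the Experiment 1 application says the objective is to "examine the effect of nicotine content (0.4 mg/g, 1.4 mg/g, 2.5 mg/g, 5.6 mg/g, and 17.4 mg/g of tobacco"). The Data Analyses text for Aim 1 says the experiment compares "behavioral economic demand intensity and elasticity of conventional cigarettes and reduced-nicotine cigarettes at five doses", that is, five doses plus one further product. Section 5.1 of the Experiment 1 application identifies that product: the participant's "preferred brand of conventional cigarettes will be used for the appropriate session". Section 5.1 also adds a seventh session with a commercial cigarette that is not the usual brand. It is always given last, and the power text does not include it.

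For intensity and elasticity, the mixed models use cigarette type as the factor. No test restricted to the five doses is specified for these outcomes, and no power is given for one.

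**The concern.** The power is attributed to a dose factor with six levels, and the design has no such factor. The usual brand differs between participants. Section 5.1 of the Experiment 2 application puts conventional cigarettes at about 16 to 19 mg/g, a range that contains the 17.4 mg/g study cigarette. A difference between those two would therefore reflect product or brand at least as much as nicotine content.

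Two things follow. A reader who takes the 80% as the chance of detecting a nicotine-content effect is reading the power of a different test. And an overall test on six cigarette types can be significant because the usual brand stands apart from the study cigarettes while the five doses are equal. Both matter because the plan intends regulators to use the results to set policy by nicotine dose.

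**Working it through.** **Inputs.** From the Experiment 1 Sample Size Justification: n = 36, f = 0.175, alpha = 0.05, m = 6 levels. From Section 2.1 and the Aim 1 Data Analyses: five doses, so m = 5 for a dose test. Assumed, because not stated: correlation rho = 0.5 and sphericity (epsilon = 1).

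**Formula.** For a one-group within-factors ANOVA, the noncentrality is lambda = f² × n × m / (1 − rho), with df m − 1 and (n − 1)(m − 1).

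**Step 1: reproduce the plan.**
- Experiment 1, m = 6: lambda = 0.030625 × 36 × 6 / 0.5 = 13.23, df 5 and 175, power 79.97%. The stated 80% reproduces.
- Experiment 2 (n = 30 per dose, m = 4, f = 0.25): lambda = 0.0625 × 30 × 4 / 0.5 = 15.0, df 3 and 87, power 90.4%. The stated 90% reproduces, which supports the assumed rho and epsilon.
- Sensitivity for m = 6: 71.1% at rho = 0.4 and 89.1% at rho = 0.6, so the stated figure points to rho of about 0.5 under sphericity.

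**Step 2: five doses, f = 0.175 across those five.** lambda = 0.030625 × 36 × 5 / 0.5 = 11.03, df 4 and 140, power 74.7%. With n = 36, 80% is reached at f of about 0.185. At f = 0.175, 80% needs 41 completers. Over rho = 0.4 to 0.6, the five-level power runs from 65.7% to 84.7%.

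**Step 3: f = 0.175 defined across six levels instead.** Let D be the distance, in within-condition SDs, from the usual-brand mean to the average of the five dose means. Splitting the variance of the six means gives f6² = (5/6) f5² + (5/36) D², so f5² = 1.2 × f6² − D²/6. With f6 = 0.175, 1.2 × f6² = 0.03675.

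| Pattern of means, f6 = 0.175 | f over five doses | Power of five-dose test |
|---|---|---|
| Usual brand at the dose average (D = 0) | 0.192 | 83% |
| Only 0.4 mg/g lower, usual brand equal to 17.4 | 0.188 | 81% |
| 0.4 and 1.4 mg/g lower, usual brand equal to 17.4 | 0.182 | 78% |
| Equal steps up the five doses, usual brand equal to 17.4 | 0.166 | 70% |
| Only 17.4 mg/g and usual brand higher | 0.148 | 58% |
| Only the usual brand differs | 0 | 5% (alpha) |

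On this definition the dose test keeps 80% power only if f5 is at least 0.185. That requires D² ≤ 6 × (0.03675 − 0.0343) = 0.0147, so D of at most about 0.12 SD.

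**Step 4: the six-level test with all five doses equal.** If only the usual brand differs, by d SDs, then f6 = d × √5 / 6. Rejection is 37.9% at d = 0.3, 64.0% at d = 0.4 and 80% at d = 0.47 (0.47 × 2.236 / 6 = 0.175). The whole effect size for which the study is powered can arise with no dose effect.

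**The case against.** The strongest reply is that the power calculation matches the factor the plan models. Five doses plus conventional cigarettes make six cigarette types, the mixed models use cigarette type, and the 80% is correct for that test; the only slip is the word in brackets. This stands as far as the arithmetic goes. It does not supply a power for the dose comparison, which is what the same paragraph gives as the reason for 36 completers.

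A reader might infer that the dose comparison simply has 75% power, or that counting a sixth level always inflates power. The documents support neither. The f of 0.175 is a conventional midpoint between small and medium and is not tied to either set of levels; Step 3 shows the five-dose figure can fall on either side of 80%.

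A reader might also infer that participants will recognise their own brand, so that this condition is unblinded. That is plausible but is not stated. The blinding text covers dose and nicotine content and does not say whether the usual brand's identity is masked. No calculation here depends on it.

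Finally, the plan nowhere says that one significant overall test would prove a dose effect. It also intends to separate doses that share a unit-price curve from those that do not, and to analyse demand against plasma nicotine. That is fair, and it limits the point to a missing specification. A mixed model allows a five-dose contrast, but none is named in advance for intensity or elasticity.

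**Conclusion.** The point holds in limited form. The plan gives 80% power to a six-level dose factor, and the design has five doses and a usual-brand comparator. For the six-level cigarette-type test the 80% is right. For the dose comparison, at the same f over five doses, power is about 75% (a shortfall of about 5 points, or 5 completers), with 80% at f of about 0.185. If f is defined over six levels, five-dose power varies with the pattern of means, from 58% to 83% in the examples with some dose effect and down to alpha with none.

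All these figures assume rho = 0.5 and sphericity. The loss of power is modest. The more important consequence is for interpretation: a significant six-level result is not by itself evidence of a nicotine-content effect. The text is wrong as written and should be corrected, but the study does not need redesigning.

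**What to change.** In the Experiment 1 Sample Size Justification, describe the six levels as cigarette types and state the correlation and epsilon used. In the Aim 1 Data Analyses, prespecify for intensity and elasticity a 4-df dose test restricted to the five experimental cigarettes. Report the usual brand, and the non-randomised seventh-session commercial cigarette, as separate contrasts. Restate the power of the dose test with 36 completers as about 75% at f = 0.175, or 80% at f of about 0.185, under the stated assumptions, and say which set of levels f refers to.

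The cost is wording and a slightly less favourable power figure. No participants or sessions are added. Keeping 80% at f = 0.175 for the dose test would instead take 41 completers, but the correction does not require this.

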To measure how the subjective effects and plasma nicotine levels dissipate over the course of an hour, VAS ratings and blood draws will be collected immediately after the 5-minute administration period at minute 10, and again at minutes 15, 20, 30, 45, and 60. We will use closed intravenous catheter systems to avoid multiple needle sticks per session. At minute 20 (10 min after the end of the consumption period), participants will complete a hypothetical purchase task for the cigarette they just consumed, similar to the ones completed during the assessment session (see **Table 1**). Hypothetical purchase tasks are typically used to measure the consumption of a product already familiar to the participant. In this experiment, we will use this procedure in a novel way by asking participants to indicate their consumption decisions for a product they just consumed, but remain blinded to the nicotine content. This will prevent their responses from being biased by preconceptions of dose information, instead tying purchasing behavior to the experienced effects of each dose.

Participants will be compensated \$20 for the consent session, \$40 for the assessment session, \$40 for each of the six cigarette purchase sessions, and \$75 for completing all sessions for a maximum total of \$375.

Sample Size Justification

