where Q is consumption of the commodity, C is the price, Q_0 is the derived initial consumption without cost constraints (demand intensity), k is the span of the function in logarithmic units, and α is the demand elasticity. Q and C are determined by the data and k is set to a constant determined empirically by the actual data, leaving only Q_0 (demand intensity) and α (demand elasticity) as free parameters to be fitted. Analysis will proceed by fitting the above equation to individual subject data, then comparing demand intensity and elasticity consistent with the goals of each analysis. Intensity and elasticity from the demand function will be compared among the different cigarette types with nonlinear regression, as we have done previously (e.g., Koffarnus, Hall, et al., 2011; Koffarnus, et al., 2015). Then, mixed effects models will be used to characterize intensity and elasticity as a function of cigarette type. A random effect will be included to model repeated measures on subjects, and socio-economic and other demographic variables will be statistically screened for inclusion using

model-based hypothesis tests. These analyses will allow us to detect which doses fall on the same unit price curve and which doses do not and constitute a low-dose exception that we hypothesize will be related to lack of abuse liability. Additionally, we will be able to inform regulators how cigarettes at different doses are likely to affect unrestricted consumption (demand intensity) and cigarette valuation (demand elasticity).

In addition to the demand data, we will compare the VAS measures of drug effect as a function of cigarette dose to determine if these measures coincide with demand intensity, demand elasticity, or both. For these analyses, we will use mixed effects models to compare cigarette type and dose for the VAS measures and to control for the variance associated to subject in this within-subject design.

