Analyses by Nicotine Absorption. We will also analyze the demand data as a function of pharmacokinetic parameters derived from the plasma nicotine data, allowing us to determine how nicotine absorption and circulating nicotine level affects demand intensity and elasticity. From the plasma nicotine curves, we can obtain measures of C_{max} (the peak plasma nicotine concentration) and the area under the plasma nicotine concentration curve, a measure of the total nicotine exposure over a given period of time. These measures will allow us to assess demand as a function of actual nicotine exposure and provide quantitative estimates of how abuse liability of cigarettes relates to nicotine exposure. Data analyses will be carried out similarly to those above, but with the pharmacokinetic variables derived from plasma nicotine levels being the basis of comparison across doses. This will allow us to calculate demand parameters in terms of plasma nicotine instead of potentially arbitrary units like puffs or cigarettes consumed. Expressing demand in terms of plasma nicotine is important as it will allow us to project what the relative abuse liability and consumption of cigarettes would be across a range of obtained nicotine concentrations, independent of particulars of nicotine delivery among users or cigarettes (i.e., control for nicotine absorption by the lungs, puff velocity, etc.). This information would be very valuable to regulators, as it would allow them to create policy based on nicotine dose.

Expected Results

Understanding how demand for nicotine products relates to nicotine content and nicotine absorption is important for the effective regulation of nicotine content. We expect that demand will be related to plasma nicotine levels and nicotine content of the cigarettes, but that this will not be a strict one to one relationship. We expect this relationship to be more straightforward between the 5.6 and 17.4 mg/g doses, but that this will become less clear and break down at small doses approaching 0 mg/g (i.e., a low-dose exception). In Specific Aim 1, we will quantify this relationship between dose and demand, which will also result in the quantification of the demand associated with cigarettes delivering negligible nicotine.

Experiment 2: Model Potential Regulatory Environments with our Experimental Tobacco Marketplace

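### The Experiment 1 VAS model has no demand term and the plan sets no criterion for *coincide*, so whether VAS tracks intensity, elasticity or both rests on an informal comparison of dose profiles

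*Combined protocol and SAP*

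**What the plan says.** Three parts of the Experiment 1 plan bear on this.

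- **The question.** Under Data Analyses, Demand Analyses by Nicotine Content: "we will compare the VAS measures of drug effect as a function of cigarette dose to determine if these measures coincide with demand intensity", elasticity, or both.
- **The method for it.** The next sentence reads "we will use mixed effects models to compare cigarette type and dose for the VAS measures", and adds that the models serve "to control for the variance associated to subject in this within-subject design". Nothing further is said about VAS.
- **The demand models.** In the same subsection, "Analysis will proceed by fitting the above equation to individual subject data" gives intensity (Q0) and elasticity (alpha) for each subject, and then "mixed effects models will be used to characterize intensity and elasticity as a function of cigarette type". These models have no VAS term.

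VAS ratings are taken after smoking "at minute 10, and again at minutes 15, 20, 30, 45, and 60". On the purchase task, the plan says: "At minute 20 (10 min after the end of the consumption period), participants will complete a hypothetical purchase task". No VAS summary or time point is named for analysis.

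The next subsection, Analyses by Nicotine Absorption, takes a direct route for another session-level measure: "We will also analyze the demand data as a function of pharmacokinetic parameters derived from the plasma nicotine data". No equivalent is written for VAS.

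**The concern.** The question concerns a relation between two sets of measures, but each planned model contains only one of them. The link is left to the reader, who must look at VAS by cigarette, then intensity by cigarette, then elasticity by cigarette, and decide which patterns resemble each other. No rule for resemblance is stated.

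Two things are at stake. First, the choice among intensity, elasticity and both is weakly determined: if both demand parameters move with dose, a VAS score that moves with dose will resemble both. Second, six post-smoking ratings and more than one VAS measure are available, so with no item or time named the comparison could be shaped after the data are seen. The design's stated rationale is that purchasing reflects the effects just experienced. A session-level link between VAS and demand is therefore of direct interest, and the collected data can supply it.

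**Working it through.** **1. Terms in each model.**

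| Analysis | Outcome | Explanatory terms | Links VAS to demand? |
|---|---|---|---|
| VAS | VAS | cigarette type, dose, subject | No |
| Demand by content | Q0, alpha | cigarette type, subject, screened demographics | No |
| Demand by absorption | Q0, alpha | Cmax, AUC | No, but it shows the form such a model could take |

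**2. The plan's own figure.** No figure is given for the VAS question. The Sample Size Justification gives 36 completers for 80% power at f = 0.175 with six repeated measures and alpha = 0.05. Assuming a correlation among measures of 0.5 and sphericity (neither is stated):

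- noncentrality = f² × n × m / (1 - rho) = 0.030625 × 36 × 6 / 0.5 = 13.23
- df = 5 and 35 × 5 = 175
- power = 0.7997

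The figure reproduces. It concerns demand across doses and is not in question here; it supplies n = 36 and m = 6 for what follows.

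**3. What the planned comparison can and cannot show.** The simulation used 36 subjects × 6 cigarettes and 3,000 runs per setting. Assumed inputs were dose means of -0.6, -0.35, -0.1, 0.1, 0.35 and 0.6, and unit residual and subject SDs. *Residual r* is the within-person VAS-demand correlation after dose is removed.

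| Demand dose profile | Residual r | Median F, VAS on cigarette | Mean correlation of six means | Share of runs above 0.811 |
|---|---|---|---|---|
| Same as VAS | -0.5 | 8.0 | 0.84 | 68% |
| Same as VAS | 0 | 7.9 | 0.89 | 87% |
| Same as VAS | +0.5 | 8.0 | 0.95 | 99% |
| Flat | 0 | 8.05 | 0.01 | 3% |
| Flat | +0.5 | 8.0 | 0.15 | 5% |

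The value 0.811 is the two-sided 5% critical correlation for six points: t(4) = 2.776, and 2.776 / √(2.776² + 4) = 0.811.

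- The VAS model alone gives the same result whatever demand does.
- The side-by-side profiles do separate a matching profile from a flat one.
- They hardly register the within-person relation: a residual r of -0.5 still gives a profile correlation of 0.84.

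**4. Intensity versus elasticity.** Suppose Q0 and alpha both change steadily with dose. Each set of six means then correlates strongly with the six VAS means, positively or negatively, and the profiles give no basis for choosing between them.

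**5. What a linking model would estimate.** Take the matching-profile inputs above. The sum of squared dose means is 0.985, and there are 5 within-subject df per person. The overall within-subject correlation is then approximately (0.985 + 5r) / (0.985 + 5):

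- residual r = -0.5: -1.515 / 5.985 = -0.25
- residual r = 0: 0.985 / 5.985 = 0.16
- residual r = +0.5: 3.485 / 5.985 = 0.58

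The overall association thus combines dose-driven and other covariation. The cigarette-adjusted association isolates the second part; in the simulation it averaged -0.50, 0.00 and 0.50.

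**6. Precision of the adjusted association.** Removing subject and cigarette effects leaves 35 × 5 = 175 df, so Fisher's z has variance of about 1/(175 - 2) = 1/173. Power = Φ(atanh(r) × √173 - 1.96), with √173 = 13.153:

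- r = 0.20: 0.2027 × 13.153 = 2.667; Φ(0.707) = 0.76
- r = 0.25: 0.2554 × 13.153 = 3.359; Φ(1.399) = 0.92

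**The case against.** The strongest reply is that the plan asks a dose-level question. VAS is to be compared as a function of dose, demand is modelled on the same factor in the same subsection, and agreement of the two profiles is the natural sense of *coincide*. On that reading the parallel models do bear on the question, and step 3 supports this: when effects are strong, matching and flat profiles are readily told apart. Within-person association would then be an additional estimand that the plan never promised.

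Much of this stands. A reader might infer that the plan cannot answer its VAS question at all, or that any conclusion would be unsupported. The documents do not bear that out, because a dose-level statement would have support. A reader might also suppose that coincidence will be declared when both dose tests are significant. The plan states no such rule, and its models give estimates by cigarette that can be compared directly. Nor is the VAS model on cigarette type alone; it names cigarette type, dose and subject.

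What the reply does not supply is a criterion for profile agreement, a way to distinguish intensity from elasticity when both move with dose, or a named VAS item and time. It is also fair to say that a model adjusted only for cigarette would remove the dose-driven covariation the plan has in mind. For that reason the fix puts the unadjusted association first.

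**Conclusion.** The concern holds in limited form. The VAS model has no demand term and the plan gives no joint analysis or criterion, so the answer depends on an informal reading of separate dose profiles built on six cigarette means. That reading can show whether both measures change with dose. It cannot choose between intensity and elasticity when both do, and it cannot show association within people.

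The structural point follows from the model terms and needs no assumption. The simulated sizes rest on assumed linear dose means and unit SDs. The power figures rest on assumed correlations of 0.20 and 0.25 and on the 36 completers and six measures in the Sample Size Justification. Section 5.1 of the Experiment 1 IRB application lists a seventh, non-usual-brand cigarette, which is not counted here.

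This is a worthwhile, low-cost improvement to a supplementary analysis. The sample size and the demand and pharmacokinetic analyses are unaffected.

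**What to change.** 1. Keep the VAS-by-cigarette mixed model as the description of VAS across doses.
2. Name one VAS drug-effect item in advance and use its minute-20 rating, the time the Experiment 1 plan gives for the purchase task. Section 5.1 of the IRB application says only that the task follows the ratings at one of the time points. If it was run at another time, use the rating that immediately preceded it.
3. For each demand parameter, fit a mixed model of ln Q0 or ln alpha on that score, centred within subject, with a subject random effect.
4. Report the overall within-subject association, which includes dose-driven covariation, as the main answer to *coincide*. Report the association adjusted for cigarette as secondary. Give 95% confidence intervals for both.
5. Base the statement on intensity, elasticity or both on these estimates and intervals, read beside the dose profiles.

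The cost is one extra model per demand parameter, fitted with and without cigarette, and the need to commit to a VAS item before analysis. No new data are required.
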